#### Test product, dose and mode of administration:

BCX7353 capsules, to be administered orally.

BCX7353 capsules contain 55 and 75 mg of the active ingredient (free base equivalents). Subjects will take the following orally QD at approximately the same time each day, with whichever meal is typically the largest of the day:

Treatment Group 1 (110 mg QD) Parts 1 and 2: two 55-mg capsules of BCX7353 Treatment Group 2 (150 mg QD) Parts 1 and 2: two 75-mg capsules of BCX7353

Subjects randomized to Treatment Group 1 or 2 will receive the same dose in both Parts 1 and 2, for a total duration of 48 weeks of treatment during Parts 1 and 2 (24 weeks of treatment in each study part for Parts 1 and 2).

Subjects randomized to Treatment Group 3 (placebo) in Part 1 will be re-randomized to receive active study drug from the Week 24 visit (Part 2):

Treatment Group 3a (110 mg QD) Part 2: two 55-mg capsules of BCX7353

Treatment Group 3b (150 mg QD) Part 2: two 75-mg capsules of BCX7353

#### Part 3

BCX7353 capsules contain 110 and 150 mg of the active ingredient (free base equivalents). Subjects will take a single capsule orally once daily at approximately the same time each day, with whichever meal is typically the largest of the day.

Treatment Groups 1 and 3a (110 mg QD) Part 3: one 110-mg capsule of BCX7353

Treatment Groups 2 and 3b (150 mg QD) Part 3: one 150-mg capsule of BCX7353

Subjects randomized to Treatment Groups 1 and 2 will receive a total of up to 96 weeks of active BCX7353 treatment. Subjects randomized to Treatment Group 3 will receive a total of up to 72 weeks of active BCX7353 treatment.

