Beginning at screening and through the Week 48 visit, details of acute attacks of angioedema will be recorded in an electronic diary (e-diary). Attacks will be treated in accordance with the subject's normal standard of care. Within approximately 2 business days of the end of each attack that occurs from the screening visit through the Week 48 visit, subjects will be contacted by the Investigator (or appropriately trained designee) to discuss the clinical characteristics of the attack, any questions on the entered data or to gain additional attack details not included in the e-diary that the Investigator deems important to clinically evaluate the event, as applicable. This information, in conjunction with the e-diary record, will be used by the Investigator to verify or reject the event recorded in the diary as an HAE attack. All Investigator-confirmed attacks of HAE must include symptoms of swelling; prodromal symptoms in the absence of swelling are not considered HAE attacks, regardless of treatment. Symptoms of swelling, in addition to visible swelling, may also include symptoms in the oropharyngeal or abdominal regions, which are indicative of internal swelling.

The main study will be comprised of adult subjects ( $\geq 18$  years of age); a substudy in participating regions will allow adolescent subjects ( $\geq 12$  to 17 years of age) to enroll. Main study and substudy subjects will be randomized via a separate randomization scheme; however, study-mandated procedures will be identical, and the analyses will include all subjects who participate in the study.

Study visits in Part 1 will occur at screening, baseline and Weeks 2, 4, 8, 12, 18 and 24. The primary efficacy analysis will occur after the last subject completes the Week 24 visit and will include all data through Week 24. Subject treatment will remain blinded to the subjects, site staff, and Sponsor staff who interact with sites on a regular basis during Part 2.

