# Part 2 (24-week evaluation of safety of blinded BCX7353)

Part 2 of the study will start with the administration of study drug dispensed at the Week 24 visit. Subjects in Groups 1 and 2 will continue to receive the same BCX7353 dose to which they were randomized in Part 1 of the study in a blinded manner. Subjects randomized to Group 3 will undergo a second randomization in a 1:1 ratio to receive either a 110 mg QD dose or 150 mg QD dose of BCX7353 in a blinded manner beginning at the Week 24 visit (see Figure 1). The active dose a subject receives in Part 2 will be blinded for all subjects; subjects will be informed that they will receive an active dose of BCX7353 in Part 2.

Study visits in Part 2 will occur during Weeks 26, 28, 32, 36, and 48 with telephone contact at Weeks 40 and 44. Subjects will continue to document all angioedema attacks that occur while on study drug in their e-diary. Investigator confirmation of attacks will continue to be required for Part 2. Interim safety analyses will be conducted while Part 2 is ongoing to support regulatory filings.

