# Part 3 (48-week evaluation of safety of open-label BCX7353)

Part 3 of the study will start with the administration of the study drug dispensed at the Week 48 visit. Subjects will continue to receive the same BCX7353 dose in Part 3 to which they were randomized in Part 2 of the study in an open-label manner. Once Part 1 results are available, all subjects in Part 3 may be moved to a single dose level of BCX7353, based on the data from Part 1, if appropriate.

Study visits in Part 3 will occur during Weeks 60, 72, 84, and 96, with telephone contact at Weeks 52, 56, 64, 68, 76, 80, 88, and 92.

Subjects will continue to document all angioedema attacks that occur in a paper diary throughout Part 3 and will have regular visits to assess safety and tolerability. Investigator confirmation of attacks will not be required for Part 3. All attacks recorded by the subjects will be reviewed and confirmed or rejected according to a set of pre-defined rules prior to inclusion in effectiveness analyses. These rules, which were constructed in concert with HAE-treating physicians, will be outlined in this SAP.

A final study follow-up visit will be scheduled approximately 3 weeks following the last administration of study drug (Week 99).

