- c The Week 2 visit will consist of monitoring liver function tests only (ALT, AST, GGT, total and direct bilirubin, ALP); urine and additional tubes of blood may be required to accommodate possible reflex testing for abnormal GGT, AST or ALT. If preferred by the subject and clinical site, laboratory values may be drawn and resulted locally, with results entered into the CRF.
- d The last visit in Part 1 (Week 24) must occur the day following 24 weeks of study drug dosing in Part 1.
- e The Investigator (or designee) must call and talk to the subject at least weekly in between the Screening and Baseline visits and on-treatment during through Week 24; alternative forms of interactive communication such as returned email and cellular text correspondence are acceptable. During all calls, the

investigator (or designee) will assess the subject's overall wellbeing, discuss compliance (if applicable), proper recording of attack details (if applicable), or any usability issues with the e-diary. A weekly phone call may be omitted if the subject records an attack as the Investigator must call and confirm or reject the attack (see Footnote 'x').

- f An HAE medical history form will be completed by the subject at screening. Medical and medication history will be taken at screening and updated at baseline.
- g BMI calculation and height at screening; weight is to be recorded at each scheduled in-clinic visit during Part 1 except at Week 2.
- h The protocol lists parameters to be assessed.
- i Full physical examinations will be performed at Screening, Baseline and Week 24; abbreviated physical examinations targeted to signs and symptoms will be performed at all post-baseline visits except for Week 2.
- j For women of childbearing potential (including adolescents), regardless of contraception or lifestyle, a serum pregnancy test will be administered at screening, urinary pregnancy tests will be assessed at all subsequent visits as indicated in the table. Demonstration of a negative urine pregnancy test will be required prior to the subject taking study drug on Day 1. In addition to urine pregnancy tests at study visits, women of childbearing potential who enroll at sites in Europe will be dispensed urinary pregnancy tests to be completed at home at Weeks 16 and 22. Sites will confirm negative test results by telephone and record the results in source documents.

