b The Week 26 visit will consist of monitoring liver function tests only (ALT, AST, GGT, total and direct bilirubin, ALP); urine and additional tubes of blood may be required to accommodate possible reflex testing for abnormal GGT, AST or ALT. If preferred by the subject and clinical site, laboratory values may be drawn and resulted locally, with results entered into the CRF.

- c The Investigator (or designee) must call and talk to the subject during Week 40 and 44; alternative forms of interactive communication such as returned email and cellular text correspondence are acceptable. During all calls, the investigator (or designee) will assess the subject's overall wellbeing, discuss compliance (if applicable), proper recording of attack details (if applicable), or any usability issues with the e-diary. The phone call may be omitted if the subject records an attack as the Investigator must call and confirm or reject the attack (see Footnote 'm').
- d Abbreviated physical examinations targeted to signs and symptoms will be performed at post-baseline visits.
- e To include blood pressure and pulse rate. Prior to obtaining vital signs, subjects should rest in a supine position for at least 5 minutes.
- f The protocol lists parameters to be assessed.
- g ECGs may be single assessments. Prior to obtaining an ECG, subjects should rest quietly in a supine position for at least 10 minutes. ECGs should be obtained prior to any blood sampling. An ECG should be repeated for a change from baseline in QTcF > 60 msec or a QTcF interval > 500 msec.
- h The EQ-5D-5L will be administered once at baseline and 1 to 2 × at Weeks 28, 32, 36, and 48. The subject will fill out the first EQ-5D-5L at baseline and on-study to describe their current health state today as instructed per the instrument. The subject will also fill out a second EQ-5D-5L based on a recollection of their health state during an average attack that they experienced since the last study visit. If the subject has not had an attack since their last study visit, the subject is not required to fill out the second, attack-related EQ-5D-5L.
-  Where possible, QoL and health outcome questionnaires should be collected as the first assessments at a visit.
- j Any issues (including mediocre or poor compliance) warranting e-diary re-education should occur on an as-needed basis.

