### 10.1.4. Summaries of Adverse Event Incidence Rates per 100 Person-Years of Exposure to Study Treatment

For this study, the duration of exposure to study treatment will vary depending on whether the subject is initially assigned to placebo. Because of this, certain TEAE tables will be repeated using the number of TEAEs per 100 person-years of exposure instead of using a count, where 1 year = 365.25 days of exposure. These tables will not be created for the Part 1 primary efficacy analysis since the same amount of exposure is expected per treatment group for Part 1 analysis.

To determine the rate of TEAEs per person-year of exposure, the duration of treatment exposure will be computed for each subject and treatment. The rate of TEAEs per person-year will then
be calculated as the count of TEAEs divided by the duration of treatment exposure. This value will then be multiplied by 100 to compute the rate per 100 person-years of exposure. For subjects initially randomized to placebo, there will be exposure time for placebo treatment and a separate exposure time for treatment with either 110 or 150 mg. The total exposure for the treatment group of interest will sum the individual subject exposure time for each treatment group.

The following summary tables of rate of TEAEs per 100 person-years of exposure will be provided by treatment group (by SOC and PT):

- Summary of TEAE rate per 100 person-year of exposure
- Summary of drug-related, TEAE rate per 100 person-year of exposure
- Summary of TESAEs per 100 person-year of exposure

A listing of exposure to study treatment in 100 person-years will be provided by subject and treatment.

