14.3.5.17	Safety - Subjects with Prior Androgen Use	Summary of Elevations in Post-baseline Liver Function Tests, Part 1
14.3.5.17.ES	Safety - Subjects with Prior Androgen Use	Summary of Elevations in Post-baseline Liver Function Tests, Entire Study
14.3.5.18	Safety - Subjects with No Prior Androgen Use	Summary of Elevations in Post-baseline Liver Function Tests, Part 1
14.3.5.18.ES	Safety - Subjects with No Prior Androgen Use	Summary of Elevations in Post-baseline Liver Function Tests, Entire Study
14.3.5.19	Safety	Summary of Treatment-Emergent Elevations in Post-baseline Liver Function Tests, Part 1
14.3.5.19.ES	Safety	Summary of Treatment-Emergent Elevations in Post-baseline Liver Function Tests, Entire Study

Output #	Population	Output Title
14.3.5.25	Safety	Time to First Occurrence of Grade 3 or 4 ALT, Part 1
14.3.5.27	Safety	Time to First Occurrence of Grade 3 or 4 AST, Part 1
14.3.5.29	Safety	Time to First Occurrence of Grade 3 or 4 Total Bilirubin, Part 1
14.3.5.31.ES	Safety	Summary of Rate of Elevations in Post-baseline Liver Function Tests Per 100 Person-Years of Exposure, Entire Study
14.3.6.1	Safety	Summary of Observed and Change from Baseline Vital Signs, Part 1
14.3.6.1.ES	Safety	Summary of Observed and Change from Baseline Vital Signs, Entire Study
14.3.7.1	Safety	Summary of Observed and Change from Baseline ECG Interval Values, Part 1
14.3.7.1.ES	Safety	Summary of Observed and Change from Baseline ECG Interval Values, Entire Study
14.3.7.2	Safety	Summary of ECG Findings, Part 1
14.3.7.2.ES	Safety	Summary of ECG Findings, Entire Study
14.3.7.3	Safety	Summary of QTcF Observed and Change from Baseline Categorical Findings, Part 1
14.3.7.3.ES	Safety	Summary of QTcF Observed and Change from Baseline Categorical Findings, Entire Study
14.4.1.1	ITT	Summary of WPAI Scores, Part 1
14.4.1.1.ES	ITT	Summary of WPAI Scores, Entire Study
14.4.1.4	ITT	Summary of Responses to WPAI Individual Questions, Part 1
14.4.1.4.ES	ITT	Summary of Responses to WPAI Individual Questions, Entire study
14.4.2.1	ITT	Summary of EQ-5D-5L VAS Scores, Part 1
14.4.2.1.ES	ITT	Summary of EQ-5D-5L VAS Scores, Entire Study
14.4.2.4	ITT	Summary of EQ-5D-5L VAS Scores from Usual Attack, Part 1
14.4.2.4.ES	ITT	Summary of EQ-5D-5L VAS Scores from Usual Attack, Entire Study
14.4.2.7	ITT	Summary of EQ-5D-5L Index Scores, Part 1
14.4.2.7.ES	ITT	Summary of EQ-5D-5L Index Scores, Entire Study
14.4.2.10	ITT	Summary of EQ-5D-5L Index Scores from Usual Attack, Part 1

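### The entire-study liver-test table divides elevations by person-years although scheduled testing thins to one third by Part 3, so its columns are not comparable

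*SAP*

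**What the plan says.** The display is named in the table list of SAP 17.1 as "Summary of Rate of Elevations in Post-baseline Liver Function Tests Per 100 Person-Years of Exposure, Entire Study". It has no Part 1 counterpart, and the shells are kept in a separate document.

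- **Rate.** SAP 10.1.4 defines a person-year rate for adverse events, to "be calculated as the count of TEAEs divided by the duration of treatment exposure". It names three adverse-event tables and no liver table.
- **Counting.** SAP 10.4 counts a subject once per elevation criterion within a treatment group, on the worst result.
- **Part 1 schedule.** "Study visits in Part 1 will occur at screening, baseline and Weeks 2, 4, 8, 12, 18 and 24". Table 2 makes Week 2 a liver visit: "The Week 2 visit will consist of monitoring liver function tests only (ALT, AST, GGT, total and direct bilirubin, ALP".
- **Part 2 schedule.** "Study visits in Part 2 will occur during Weeks 26, 28, 32, 36, and 48 with telephone contact at Weeks 40 and 44". Table 3 does the same for Week 26: "The Week 26 visit will consist of monitoring liver function tests only (ALT, AST, GGT, total and direct bilirubin, ALP".
- **Part 3 schedule.** "Study visits in Part 3 will occur during Weeks 60, 72, 84, and 96". Contacts between these visits are by telephone.
- **Exposure.** "Subjects randomized to Treatment Groups 1 and 2 will receive a total of up to 96 weeks of active BCX7353 treatment". Subjects first given placebo receive up to 72 weeks of active drug (Technical Summary Report).
- **Columns.** Table 7 offers a placebo column holding Part 1 data only, and notes that a given table need not use every column.
- **Purpose.** SAP 6.1, below Table 8, explains that person-year displays may be added because active exposure is shorter for subjects who began on placebo.

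No section adjusts a laboratory rate for how often the test was done.

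**The concern.** Dividing by time on treatment treats every week as equally observed. That is reasonable for events a subject can report on any day. A raised ALT, AST or bilirubin is recorded only if a sample is taken while it is raised.

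Placebo time lies wholly in the most densely tested period, while up to half of the originally active subjects' time, and two thirds of the after-placebo subjects' active time, lies in the sparsest. The active rate is then diluted by thinly tested weeks and the placebo rate is not. At stake is a descriptive liver-safety figure that could look favourable to the drug for reasons of scheduling alone. The two active columns that the person-year adjustment is meant to put on the same footing also differ in testing density.

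**Working it through.** The SAP states no figure for this quantity, so there is none to reproduce. All inputs come from the SAP for Study BCX7353-302; the protocol supplied is for Study BCX7353-202.

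**Scheduled post-baseline liver tests (Tables 2 to 4)**

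| Period | Weeks of draws | Tests / weeks | Per week |
|---|---|---|---|
| Part 1 | 2, 4, 8, 12, 18, 24 | 6 / 24 | 0.250 |
| Part 2 | 26, 28, 32, 36, 48 | 5 / 24 | 0.208 |
| Part 3 | 60, 72, 84, 96 | 4 / 48 | 0.083 |

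Part 1 density divided by Part 3 density is 0.250 / 0.083 = 3.0.

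**Null ratio for short-lived elevations.** Assume an inert drug, an equal and independent chance of elevation at each test, every elevated test counted, and full completion. Expected elevations are then proportional to tests, so the ratio is (tests per week on active) / (tests per week on placebo).

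- Originally active: (15/96) / (6/24) = 0.625, or 37.5% lower.
- After placebo: (9/72) / (6/24) = 0.50, or 50% lower.
- Each dose pooled, with 40 originally active and 20 after placebo: (40×15 + 20×9) / (40×96 + 20×72) = 780/5280 = 0.148 per week; 0.148 / 0.250 = 0.591, or 41% lower.
- After placebo against originally active: (9/72) / (15/96) = 0.80.

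Without Part 3 the distortion is small: originally active (11/48) / (6/24) = 0.92, and pooled (40×11 + 20×5) / (40×48 + 20×24) / 0.250 = 0.90. Most of it comes from Part 3.

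**Duration of elevations.** Suppose new episodes start at a constant rate, last D weeks and count once when detected. In a gap of g weeks between tests, a share min(D, g)/g is detected. At D = 8, Part 1 detects everything (longest gap 6 weeks). Originally active subjects have (24 + 20 + 32)/96 = 0.792 detected, and after-placebo subjects (20 + 32)/72 = 0.722.

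| D (weeks) | Originally active | After placebo | Pooled |
|---|---|---|---|
| up to 2 | 0.625 | 0.50 | 0.591 |
| 4 | 0.65 | 0.53 | 0.62 |
| 6 | 0.69 | 0.58 | 0.66 |
| 8 | 0.79 | 0.72 | 0.77 |
| 12 or more | 1.00 | 1.00 | 1.00 |

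**Once-per-subject counting (SAP 10.4).** With k tests in w weeks and chance p per test, the rate is [1 − (1 − p)^k] / w.

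- At p = 0.05, originally active: (1 − 0.95^15)/96 = 0.00559; placebo: (1 − 0.95^6)/24 = 0.01104; ratio 0.51.
- Pooled ratios are 0.589 at p = 0.001, 0.569 at 0.01 and 0.495 at 0.05, that is 41%, 43% and 50% lower.
- If the same subjects are always elevated, the pooled ratio is (60/5280) / (1/24) = 0.27, or 73% lower. This end of the range comes from counting once over longer exposure, not from test density.
- In that last case the after-placebo column would exceed the originally active one: (1/72) / (1/96) = 1.33. The 0.80 therefore belongs to the short-lived case.

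**Other assumptions, short-lived case.** Counting the off-drug Week 99 test gives 0.67, 0.56 and 0.64. Assuming 20% dropout per 24 weeks gives 0.69, 0.53 and 0.65.

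**After a split by part.** With full completion, every column has 6/24 in Part 1, and both active columns have 5/24 in Part 2 and 4/48 in Part 3. The null ratio between columns is 1.00 within each part.

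**The case against.** The strongest reply is that a like-for-like comparison is already planned. Tables 14.3.5.14 to 14.3.5.19 each include a Part 1 version of the liver displays, in which all arms share the same 24 weeks and test schedule, and Part 1 time-to-event displays for Grade 3 or 4 ALT, AST and bilirubin are also listed. This stands, and it limits the consequence.

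Second, the SAP gives only a title. A placebo column is available but not confirmed for this table, no ratio or test is planned for it, and safety analysis is described as primarily descriptive. This also stands. It does not rescue the pooled rate, because the active columns differ in density even with placebo left out.

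Third, SAP 10.1.4 covers adverse events only, so it cannot be taken as the method for this table. That is correct, and it leaves the table's numerator and columns undefined.

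Fourth, a per-test denominator is no general cure. For new episodes of 12 weeks or more, person-years is the right scale and a per-test rate would inflate Part 3 threefold. Under once-per-subject counting at 5% per test, the per-test null ratio for originally active subjects is still [(1 − 0.95^15)/15] / [(1 − 0.95^6)/6] = 0.81. For that reason the fix asks for the number of tests to be shown, not for it to replace exposure time.

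**Conclusion.** The point holds as a defect of one display. Table 14.3.5.31.ES pools periods with a threefold difference in testing density, and nothing in the SAP corrects for it. For short-lived elevations and full completion, the null rate against placebo is about 40% low (0.625, 0.50 and 0.59), and after-placebo against originally active is 0.80. The SAP gives neither the frequency nor the duration of elevations, so the placebo distortion can only be given as a range, from 0% to about 73%.

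Three stronger readings are tempting and not supported:

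- *That an inert drug would certainly appear to cut elevations by 40%.* The figure needs the short-lived assumption.
- *That a true increase would be hidden from the report.* In the short-lived case a 1.7-fold increase (1/0.591) would show as about 1.0 in this table, but the Part 1 tables would not share that bias.
- *That the adverse-event rates per 100 person-years share the fault to a known degree.* Adverse events need no blood draw and are collected continuously. No size can be derived for them from the documents.

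**What to change.** In the specification of Table 14.3.5.31.ES:

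1. Show the rates separately for Parts 1, 2 and 3.
2. Limit any active-versus-placebo reading to Part 1, in line with Tables 14.3.5.14 to 14.3.5.19.
3. State the numerator: the once-per-subject rule of SAP 10.4, applied within each part, or all elevations.
4. State the columns, and show the number of liver tests performed per part beside each rate.

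Rates should still not be compared across parts without regard to the test counts. The cost is SAP wording and a period split in existing programs, with no new data and no change to the visit schedule. The single pooled entire-study contrast is lost.

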- Study drug should be taken at approximately the same time each day, with whichever meal is typically the largest of the day. Subjects are not required to take their doses at clinic visits. Subjects will take study drug in Part 1 beginning on Day 1 and will complete Part 1 dosing on Study Day 168 (day before Week 24 visit). Subjects will take Part 2 active study drug no sooner than the conclusion of the Week 24 visit on Study Day 169, after all other study procedures have been completed.
- The Investigator (or designee) will review the e-diary record of all HAE attacks that occur from Screening through Week 48 and either confirm or reject the attack as an HAE attack. At least 2 attacks that occur during the run-in period must meet the requirements outlined in Footnote 'n' in order to qualify the subject to randomize in the study. For all attacks that occur, subjects will be contacted within approximately 2 business days of the end of the attack to discuss the clinical characteristics of the attack, any questions the Investigator has on the entered data or to gain additional attack details not included in the e-diary that the Investigator deems important to clinically evaluate the event, as applicable. This information, in conjunction with the e-diary record, will be used by the Investigator to verify or reject the event recorded in the diary as an HAE attack. The e-diary data review, subject contact summary, and Investigator verification of the attack will be documented in the source records; the Investigator attack verification (confirmed or rejected) will also be recorded.
- y PK and PD blood samples will be drawn on all subjects with no particular relationship to the timing of study drug dosing. The Investigator (or designee) must ensure that the time of the last dose prior to PK and PD draw is recorded in the subject's e-diary (this may also be captured in the CRF).

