## 11. PHARMACOKINETICS

Analyses of concentration data will be performed using the safety population. PK concentration data will be listed by subject, treatment, day, and time for Part 1 and this will be repeated for the entire study period for the analysis at the end of the study. Note that PK concentration data collected at each visit will not be summarized by visit as the timings of PK data collected was not pre-specified.

The following summary displays will be produced:

- Summary of number and percentage of collected samples  $> 4 \times$  half-maximal effective concentration (EC50),  $> 6 \times$  EC50, and  $> 8 \times$  EC50 at each visit and overall
- Summary of number and percentage of samples within a subject >  $4 \times EC_{50}$ , >  $6 \times EC_{50}$ , and >  $8 \times EC_{50}$

The value of  $EC_{50}$  used will be 9 ng/mL.

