## **12. PHARMACODYNAMICS**

Analyses of PD data will be performed using the PD population. Plasma kallikrein inhibition data will be expressed as percent inhibition compared to subject baseline activity (%KKI). The formula for percent inhibition is:

 $\% KKI = -\frac{postbaseline \ value - baseline \ value}{baseline \ value}$ 

where the values are the amidolytic activity (%) at each time point. Multiple assessments of amidolytic activity from samples at a single time point will be handled as described in Section 6.7.4.

%KKI data will be listed by subject, treatment, day, and time. This analysis will be conducted for Part 1 and then repeated for the entire study period for the analysis at the end of the study.

The following summary displays will be produced:

- Summary of number and percentage of collected samples with > 50% and > 80% inhibition at each visit and overall
- Summary of number and percentage of samples within a subject with > 50% and > 80% inhibition

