14.4.2.10.ES	ITT	Summary of EQ-5D-5L Index Scores from Usual Attack, Entire Study
14.4.2.13	ITT	Summary of Responses to EQ-5D-5L Individual Questions, Part 1
14.4.2.13.ES	ITT	Summary of Responses to EQ-5D-5L Individual Questions, Entire study
14.4.3.1	ITT	Summary of TSQM Scores, Part 1
14.4.3.1.ES	ITT	Summary of TSQM Scores, Entire Study
14.4.3.4	ITT	Summary of Responses to TSQM Individual Questions, Part 1
14.4.3.4.ES	ITT	Summary of Responses to TSQM Individual Questions, Entire study
14.5.1.1	Safety	Summary of Plasma BCX7353 Concentration (ng/mL), Part 1
14.5.1.1.ES	Safety	Summary of Plasma BCX7353 Concentration (ng/mL), Entire Study
14.5.2.1	Safety	Plasma BCX7353 Concentration (ng/mL) Trough Samples above Kallikrein Inhibition EC50, Part 1
14.5.2.1.ES	Safety	Plasma BCX7353 Concentration (ng/mL) Trough Samples above Kallikrein Inhibition EC50, Entire Study
14.6.1.1	PD	Summary of Plasma Kallikrein Inhibition (%), Part 1
14.6.1.1.ES	PD	Summary of Plasma Kallikrein Inhibition (%), Entire Study
14.6.2.1	PD	Plasma Kallikrein Inhibition Trough Samples above 50% and 80%, Part 1

Output #	Population	Output Title
14.6.2.1.ES	PD	Plasma Kallikrein Inhibition Trough Samples above 50% and 80%, Entire Study

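### Four PK/PD threshold tables are titled as trough samples but are filled with samples drawn at any time after dosing, so they would overstate trough coverage by an amount the documents cannot fix

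*SAP*

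**What the plan says.** **Titles.** The table list in SAP Section 17.1 contains "Plasma BCX7353 Concentration (ng/mL) Trough Samples above Kallikrein Inhibition EC50, Part 1" (14.5.2.1) and "Plasma Kallikrein Inhibition Trough Samples above 50% and 80%, Part 1" (14.6.2.1). Each has a whole-study (.ES) version with the same wording, so four titles carry the word trough.

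**Sampling.** Footnote y to SAP Table 2 states: "PK and PD blood samples will be drawn on all subjects with no particular relationship to the timing of study drug dosing". The same statement stands under Table 3 (Part 2) and Table 4 (Part 3). SAP Section 11 adds: "PK concentration data collected at each visit will not be summarized by visit as the timings of PK data collected was not pre-specified".

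**Contents.** The first threshold display in Section 11 opens "Summary of number and percentage of collected samples" and applies cut-offs of 4, 6 and 8 times EC50, by visit and overall. The EC50 "used will be 9 ng/mL". Section 12 plans "Summary of number and percentage of collected samples with > 50% and > 80% inhibition at each visit and overall". Both sections add a within-subject version.

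**Selection rule.** Neither section mentions trough or sets a post-dose window. Footnote y does require the time of the last dose before each draw to be recorded.

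**The concern.** A table of trough samples tells its reader how often concentration or inhibition was still above a target at the end of the dosing interval. Samples drawn at any time describe typical exposure instead, which is a legitimate but different and more favourable quantity. If the plan is followed as written, the second is reported under the name of the first. Characterising PD effects is a Part 1 secondary objective (SAP Section 3.1.2), so the mislabelled statement would bear on a stated aim.

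Section 11 is also uneven. It declines to summarise concentrations by visit because "the timings of PK data collected was not pre-specified", then tabulates by visit the percentage above a cut-off, which depends on timing in the same way.

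**Working it through.** The plan states no expected trough percentage, so there is no figure to reproduce. The text comparison settles the mismatch. The arithmetic below shows direction and possible size only.

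**1. Do these titles belong to these summaries?** Sections 11 and 12 each describe one set of threshold summaries. The table list has one PK and one PD threshold table, each in a Part 1 and a whole-study version. They correspond, and the samples that go in are all those collected.

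**2. Direction.** At steady state on once-daily dosing, concentration is lowest around the end of the interval. A sample taken elsewhere in the interval is on average higher, so the share above any cut-off is at least as large as at trough. Inhibition follows concentration (r = 0.921 in Study BCX7353-101, Protocol Section 5.3.1), so the PD tables move the same way.

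**3. Cut-offs.** 4 × 9 = 36, 6 × 9 = 54 and 8 × 9 = 72 ng/mL.

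**4. Inputs for an illustration**
- Steady state in healthy subjects (Protocol Section 5.4.1.2). At 500 mg daily, Cmax is 517 ng/mL and AUCtau 8230 ng·h/mL. At 350 mg daily, AUCtau is 5720 ng·h/mL and there is a value of 363 ng/mL. The protocol prints 363 as AUCtau; its units and position suggest Cmax, and it is read so here.
- Cmax/Cavg: 517/(8230/24) = 1.51 and 363/(5720/24) = 1.52. The ratio does not depend on the reading of 363 alone.
- Tmax 2 to 6 h; half-life 67 to 79 h (Protocol Section 5.3.1).
- 125 mg salt = 110 mg free base (SAP Section 4.3.1), so 150 mg free base is 150 × 125/110 = 170.5 mg salt.
- Assumed, not in the documents: exposure scales linearly from 350 mg; between-subject variation is log-normal with CV 30% or 50%; the profile rises linearly to Tmax, then falls log-linearly to 24 h.

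**5. Trough relative to average.** Solve (Ct + Cmax)/2 × Tmax + (Cmax − Ct)/ln(Cmax/Ct) × (24 − Tmax) = 24 × Cavg with Cmax = 1.52 × Cavg. For Tmax of 2, 4 and 6 h, Ct = 0.61, 0.60 and 0.59 × Cavg, a peak-to-trough ratio of 2.5 to 2.6.
- 110 mg: Cavg = (5720/24) × 125/350 = 85 ng/mL; median trough 50 to 52 ng/mL.
- 150 mg: Cavg = (5720/24) × 170.5/350 = 116 ng/mL; median trough 68 to 70 ng/mL.

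**6. Percentage above cut-off** (simulation; ranges over both CVs and the three Tmax values)

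| Dose, cut-off | At 24 h | Random 0–24 h | Random 12–24 h | Excess of 0–24 h over 24 h (points) |
|---|---|---|---|---|
| 110 mg, 36 | 76–89 | 93–98 | 89–97 | 9–18 |
| 110 mg, 54 | 40–46 | 78–85 | 66–75 | 32–44 |
| 110 mg, 72 | 11–24 | 59–63 | 40–46 | 36–52 |
| 150 mg, 36 | 91–99 | 98–100 | 97–100 | 1–7 |
| 150 mg, 54 | 69–82 | 91–97 | 85–95 | 15–22 |
| 150 mg, 72 | 43–48 | 79–86 | 68–78 | 31–43 |

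**7. A flatter profile.** If concentration fell only at the 67 h half-life, peak/trough = 2^(24/67) = 1.28. A random-time sample then exceeds trough by ln(1.28)/2 = 0.124 on the log scale on average. At a cut-off equal to the median trough (50% above), the random-time share is about Φ(0.124/0.294) = 66% for CV 30% and Φ(0.124/0.472) = 60% for CV 50%. The excess is 10 to 16 points.

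**8. Visits.** Footnotes to SAP Table 2 end Part 1 dosing on Day 168 and hold the first Part 2 dose until after the Week 24 visit. The Week 24 blood therefore precedes the next dose. At other visits subjects are not required to dose in clinic, and nothing ties the draw to the dose. By-visit percentages mix these timings.

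**The case against.** The best reply is that this is one wrong word in a list of titles. Sections 11 and 12 never claim troughs, SAP Section 6.4 allows titles to change without revising the SAP, and the table shells sit in a separate document where the label might be corrected or a window defined. The Study 302 protocol was not available either (the protocol supplied is for BCX7353-202), so a definition there cannot be excluded. This stands as a limit on certainty and makes the repair easy. It does not remove the conflict, because the SAP as written sends all collected samples to tables named for troughs.

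A second reply is that the size is conjecture. That also stands. It rests on healthy-subject data at higher doses, a simplified curve, an assumed CV and a reading of a mislabelled value. Protocol Section 5.3.1 reports slightly more than dose-proportional exposure, so linear scaling down may place both doses too high. No size was computed for the PD tables.

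Some stronger readings are tempting but not supported:
- **All samples are mid-interval or near peak.** The Part 1 Week 24 draw precedes the next dose. Draws more than 24 h after a dose, for example after a missed dose, act in the opposite direction.
- **The two doses could look different merely through clinic timing.** Part 1 is randomised and double-blind, so a systematic timing difference between arms is unlikely and only chance imbalance remains.
- **The tables exist to prove 24-hour coverage.** The documents state only an aim to characterise PD effects, and no PK or PD endpoint is listed.

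**Conclusion.** The point holds as a mismatch between label and contents. Four tables named for trough samples would be filled with samples at unspecified times after dose, and with daily dosing their percentages would overstate trough coverage. The mismatch and its direction rest on the SAP text and on once-daily dosing. The size does not: it runs from near zero where almost every trough clears the cut-off to tens of percentage points where the cut-off lies near or above the median trough, and no single figure should be quoted as the bias. The by-visit columns carry a further mixing of timings. These are descriptive displays; no hypothesis test, multiplicity step or listed efficacy endpoint changes. The issue is worth correcting because the output would otherwise state something the data do not show.

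**What to change.** Choose one of two routes.

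**(a) Relabel.** Remove the word trough from the titles of 14.5.2.1, 14.6.2.1 and their .ES versions. Describe the tables as samples collected at unspecified times after dose, and make no trough-coverage statement in the report. Section 6.4 lets titles change without a SAP revision, so the cost is negligible. What is lost is any claim about the end of the interval.

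**(b) Define trough.** Derive time since last dose for every PK and PD sample from the recorded dose time; Section 6.7.5.6 already does the equivalent for attack onset. Before the Part 1 data are unblinded, write a trough window into the SAP with both a lower and an upper limit and a reason for each. Restrict the trough tables to it, and tabulate all samples separately by time since dose. This needs one derived variable and a change to Sections 11 and 12, since it alters data handling and not just a title. The drawback is that the trough tables will rest on fewer samples, possibly too few at some visits.
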